6.6 Sub-groups

In relation to initial shock (VT/pVT) as our outcome, we will conduct sub-group analyses of:

1. Hospital handover (ROSC, CPR ongoing, not conveyed);
2. 30 days survival (died/alive);
3. Survival at discharge (died/alive).

We will assess the interaction of the treatment arm, with each of the sub-groups.

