2.3.2 Clinical outcomes

Outcomes, their time of measurement and source are shown in table 1.

[figure not shown]
Outcome	Time point of measurement	Data Source
Return Of Organised Rhythm (ROOR)	2 minutes after delivery of each shock	Defibrillator data downloads
Resulting rhythm (VF/pVT/PEA/asystole)	2 minutes after delivery of each shock	Defibrillator data downloads
Refrillation rate	At any point during out-of-hospital phase	Defibrillator data downloads

Survived event (return of spontaneous circulation (ROSC) at hospital handover)	At hospital handover	Patient status at handover recorded on electronic patient clinical record by ambulance staff
Survival to 30 days and hospital discharge	30 days and hospital discharge	Hospital patient records/ GP patient records
Neurological function (mRS score) at 30 days and hospital discharge	30 days and hospital discharge	Assessment of patient and/or clinical records by research paramedic/GP to determine mRS score

Table 1: Clinical outcomes

The ultimate aim of cardiac arrest treatment is to achieve survival with good neurological function and this is one of the prioritised outcomes making up the consensus-derived core outcome set for cardiac arrest (COSCA).[28] However, an important component of assessment of treatments for cardiac arrest in which the rhythm is shockable is establishing shock efficacy. Key steps in the pathway following successful defibrillation are shown below:

Figure 2: Pathway to survival following successful defibrillation

VF = ventricular fibrillation pVT = pulsed ventricular tachycardia ROOR = return of organised rhythm ROSC = return of spontaneous circulation

Traditionally, shock success was defined as the ability of a shock to cease the chaotic electrical activity within the heart, which underlies the mechanical state of fibrillation, within five seconds of shock delivery.[29] However, termination of fibrillation (ToF) is not a good measure of shock success since the termination of all electrical activity (i.e. asystole) would be regarded as a successful outcome whereas this is the worst possible clinical outcome. The Return of Spontaneous Circulation (ROSC) would be a preferred patient-focussed outcome but is problematic since it is

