6.2 Statistical analysis of efficacy and harms

6.2.1 Statistics and data analysis

There will not be a formal statistical analysis as the study has not been powered to assess difference in interventions. The analyses will be based on summary statistics, namely mean, standard deviation, median, interquartile ranges and missingness in the data. Where possible 95% confidence intervals will also be given.

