6.2.3.1 Summary of baseline data and flow of patients

Baseline comparability of the randomised groups will be assessed using the following variables:

- Age (median and range)
- Sex (% male)
- Location of arrest (% private residence/ public place/ other)
- Witnessed vs. unwitnessed event (% witnessed and % bystander/ EMS or other healthcare provider/ unwitnessed)
- Bystander CPR vs. no bystander CPR (of those not EMS-witnessed, % provided BCPR prior to EMS arrival)
- Type of initial rhythm (% in VF/pVT, PEA or asystole)
- Time from call to application of defibrillator (median and range)
- Aetiology of cardiac arrest (% cardiac vs. non-cardiac cause)

Flow of patients will be presented using a consort flow diagram (<http://www.consort-statement.org/>).

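### Section 6.6 uses outcomes that follow the shocks as sub-groups for an ambiguously named outcome, and plans arm interactions that conflict with sections 6.2.1 and 7.10

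*Protocol*

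**What the plan says.** Section 6.6 states: "In relation to initial shock (VT/pVT) as our outcome, we will conduct sub-group analyses of". Three items follow: handover status in three levels (ROSC, CPR continuing, not conveyed), vital status at 30 days, and vital status at discharge. The section ends: "We will assess the interaction of the treatment arm, with each of the sub-groups".

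Other sections give these variables different roles:

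- Section 2.3.2, Table 1, lists as clinical outcomes "Survived event (return of spontaneous circulation (ROSC) at hospital handover"), survival at 30 days and at discharge, and the resulting rhythm two minutes after each shock.
- Section 2.3.3 lists transport to hospital as a process outcome. Section 2.8.1 will compare conveyance between arms as a check on performance bias.
- Section 6.2.3.1 lists among the baseline variables "Type of initial rhythm (% in VF/pVT, PEA or asystole").
- Section 6.2.1 says: "There will not be a formal statistical analysis as the study has not been powered to assess difference in interventions". It allows summary statistics, with 95% confidence intervals where possible.
- Section 7.10 gives, among its reasons for having no data monitoring committee, that the data are checked for completeness and not analysed for effect.

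**The concern.** A sub-group factor should be fixed before treatment can act on it. The three factors in section 6.6 are results of the resuscitation, and the arm may influence each of them. If the outcome is the initial rhythm, the outcome and sub-group roles are the wrong way round: a baseline variable is analysed within levels of later survival. If it is the rhythm after the first shock, the arm is compared within groups selected by what happened afterwards. Either way, an arm difference seen among survivors or among deaths need not reflect anything the arm did to the rhythm.

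The outcome label adds to the problem. A shock is not a rhythm, and the bracket pairs VT with pVT where the rest of the protocol writes VF/pVT. Two analysts could choose different variables in good faith.

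This is not detail left to a statistical analysis plan. The protocol has fixed the analysis, and a plan that followed it would inherit the fault. At stake is a between-arm result that could be misread when the definitive trial is designed.

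**Working it through.** **1. Roles, section against section**

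| Variable | Role in 6.6 | Role elsewhere |
|---|---|---|
| Handover status | sub-group | ROSC at handover is a clinical outcome (2.3.2); conveyance is a process outcome (2.3.3) |
| 30-day survival | sub-group | clinical outcome (2.3.2) |
| Discharge survival | sub-group | clinical outcome (2.3.2) |
| Initial rhythm (first reading) | outcome | baseline variable (6.2.3.1) |
| Rhythm after first shock (second reading) | outcome | clinical outcome (2.3.2) |

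No other section explains or corrects section 6.6. It states no figure of its own to reproduce.

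**2. First reading: initial rhythm**

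Inputs:
- Survival of initially shockable patients, p0 = 0.209 (section 1.1).
- Survival of non-shockable patients, q = 0.072 (section 1.5.1), assumed the same in both arms.
- Survival of shockable patients in a second arm, p1 (assumed).
- Share initially shockable, s, equal in expectation in both arms, because the rhythm precedes the first study shock. The true arm odds ratio on initial rhythm is therefore 1.00.

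Odds of a shockable initial rhythm among survivors are s·p/((1−s)·q). Among deaths they are s·(1−p)/((1−s)·(1−q)). Comparing the arms, s and q cancel:

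- OR in survivors = p1/p0
- OR in deaths = (1−p1)/(1−p0)

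| p1 (assumed) | OR, survivors | OR, deaths | Ratio |
|---|---|---|---|
| 0.209 (no effect) | 1.00 | 1.00 | 1.00 |
| 0.230 (0.209 × 1.10, the relative gain used in section 1.4) | 0.230/0.209 = 1.10 | 0.770/0.791 = 0.97 | 1.13 |
| 0.314 | 0.314/0.209 = 1.50 | 0.686/0.791 = 0.87 | 1.73 |
| 0.418 (doubled) | 0.418/0.209 = 2.00 | 0.582/0.791 = 0.74 | 2.72 |

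The two middle columns are selection artefacts, since the arm changed nobody's initial rhythm.

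**3. The interaction term**

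Put the roles the right way round with p1 = 0.314. The arm odds ratio on survival is (0.314/0.686)/(0.209/0.791) = 1.73 in shockable patients and 1.00 in non-shockable patients, a ratio of 1.73. This equals the last column above. On the odds-ratio scale the three-way association is symmetric, so the interaction carries real information, but as effect modification of survival by initial rhythm.

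**4. Second reading: rhythm after the first shock**

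This was checked by simulation (2 million patients, two arms) under an assumed model. An unmeasured patient factor U is standard normal. The logit of VF persisting (R) is −0.5 − U, with no arm effect. The logit of survival is −1.2 − R + U + b·arm.

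- b = 0: arm OR on rhythm 1.00 overall, 1.01 in survivors, 1.00 in deaths.
- b = 0.7: arm OR on rhythm 1.00 overall, 1.22 in survivors, 1.18 in deaths.

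The sizes depend on the model. The check shows only that spurious effects can arise under this reading too.

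**5. How thin the table will be**

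With 30 patients per arm (section 6.1), expected survivors per arm are 30·(0.209s + 0.072(1−s)). The number of these with a non-shockable initial rhythm is 30·0.072(1−s). The share s is not given, so 60%, 75% and 90% are assumed.

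| s | Survivors per arm | Of these, non-shockable | P(at least one arm has none) |
|---|---|---|---|
| 0.60 | 4.6 | 0.86 | 0.80 |
| 0.75 | 5.2 | 0.54 | 0.93 |
| 0.90 | 5.9 | 0.22 | 0.99 |

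The last column is 1 − (1 − e)³, with e = (1 − 0.072(1−s))³⁰ = 0.42, 0.58 and 0.81.

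**The case against.** The strongest reply is that section 6.6 is a drafting slip in a feasibility study whose conclusions do not rest on it. The primary outcome is the number eligible and recruited. The secondary outcomes are adherence, completeness, acceptability and staff views. This stands, and it limits the severity.

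Four stronger readings are tempting, and the protocol does not support them:

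- **Any arm-by-survival interaction is an artefact.** It is not. Step 3 shows the same 1.73 in both directions. The artefact lies in the arm effects within sub-groups.
- **Formal hypothesis tests are planned.** Section 6.6 speaks of assessing an interaction and gives no test, model or significance level. Section 6.2.1 already permits confidence intervals, so this is not the only inferential element either. The conflict remains, because comparing arm effects across sub-groups is still an analysis of differences between interventions.
- **The outcome is certainly the pre-shock rhythm.** That is the natural reading, but Table 1 also lists rhythm after each shock. Under that reading the allocation could change the outcome, and only the objection to conditioning on later outcomes survives.
- **The sparse cells show that the roles are reversed.** They do not. The corrected table has the same empty cells, the calculation does not cover handover status, and an empty arm may still leave a contrast between the other two. Sparseness is a reason to keep the corrected table descriptive.

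**Conclusion.** Section 6.6 is wrong as written. Its sub-groups are results that follow the allocated shocks, its outcome cannot be identified with certainty, and its interaction assessment conflicts with sections 6.2.1 and 7.10.

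In the illustration, an arm with no effect on initial rhythm shows odds ratios of 1.50 in survivors and 0.87 in deaths. At the 10% relative gain in survival that section 1.4 uses, the distortion is small (1.10 and 0.97). If no arm affects survival, there is none in this illustration.

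The figures rest on assumed survival in the better arm and on 7.2% applying to patients who became shockable only later, which the protocol does not state. The 20.9% is also described in two ways: as survival of initially shockable patients in section 1.1, and of witnessed arrests given a shock in section 1.5.1. The direction of the argument does not depend on these values.

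This should be fixed. It is not critical. A reader might infer that the fault endangers the feasibility conclusions or will distort the definitive trial. The protocol does not show that.

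**What to change.** Rewrite section 6.6 as follows:

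1. Name the variable without ambiguity: initial rhythm, VF/pVT versus PEA or asystole, as in section 6.2.3.1.
2. Make it the sub-group.
3. Tabulate handover status (including survived event), survival at discharge and 30-day survival by arm within it. State that the table is descriptive only, because cells will be sparse.
4. Delete the sentence on interaction, so that the section agrees with sections 6.2.1 and 7.10.

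If the rhythm after the first shock was meant, report it by arm over all treated patients and not within survival groups. Deleting section 6.6 altogether is equally acceptable.

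The cost is a few sentences of protocol wording. Initial rhythm, handover status and survival are already collected, so no new data are needed and the sample size does not change.

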7. STUDY ORGANISATION AND OVERSIGHT

7.1 Sponsor and governance arrangements

The University of Warwick will act as sponsor for this study and University of Warwick's SOPs shall be employed.

7.2 Ethical approval

Application for approval of the study will be made to the Health Research Authority (HRA). All required ethical approval(s) for the study will be sought using the Integrated Research Application System. The study will be conducted in accordance with all relevant regulations.

Before enrolling patients into the study, the study site must ensure that the local conduct of the study has the agreement of the Ambulance Service Clinical Review Group. Recruitment into the study will not commence until all required permissions are obtained and staff have received training. Substantial amendments shall not be implemented until approved by the REC and approved by the participating site.

Annual reports will be submitted to the REC within 30 days of the anniversary date on which the favourable opinion was given, and annually until the study is declared ended. The REC will be

notified of the projected end of the study date either as 90 participants are recruited or after 24 months of patient recruitment. Should the study require premature closure by any party other than the ethics committee listed in section 6.3 the REC shall be notified within 15 days of the mandated closure date. If not halted prematurely, the REC shall be informed within 90 days via the end of study form.

The CI will submit a final report to the required authorities with the results, including any publications within one year of the end of the study.

This protocol has been peer reviewed by [name] who is an Assistant Professor in Emergency and Critical Care based at WCTU but not involved in this study. [name] research interests include cardiac arrest and clinical trials.

Review of the project has also been provided by the NIHR ICA CDRF Interview panel.

7.3 Study Registration

This study will be registered with the International Standard Randomised Controlled Trial Number (ISRCTN) Register.

7.4 Notification of serious breaches to GCP and/or study protocol

A "serious breach" is a breach which is likely to effect to a significant degree –

- (a) the safety or physical or mental integrity of the subjects of the study; or
- (b) the scientific value of the study

The sponsor will be notified immediately of any case where the above definition applies during the study conduct phase.

The sponsor will notify the research ethics committee in writing of any serious breach of:

- (a) the conditions and principles of GCP in connection with that study; or
- (b) the protocol relating to that study, as amended from time to time, within 7 days of becoming aware of that breach

7.5 Indemnity

NHS indemnity covers NHS staff, medical academic staff with honorary contracts, and those conducting the study. NHS bodies carry this risk themselves or spread it through the Clinical Negligence Scheme for Trusts, which provides unlimited cover for this risk. The University of

Warwick provides indemnity for any harm caused to participants by the design of the research protocol.

7.6 Study timetable and milestones

	Month	Recruitment
Set-up	1-3	n/a
Recruitment	4-24	90
Qualitative study	12-16	30-40
Follow up	5-25	n/a
Analysis	26-29	n/a

7.7 Administration

The study co-ordination will be based at WMS/WCTU, University of Warwick.

7.8 Study Management Group (SMG)

The Study Management Group, consisting of the project staff and co-investigators involved in the day-to-day running of the study, will meet monthly throughout the project. Significant issues arising from management meetings will be referred to the Study Oversight Committee or Investigators, as appropriate.

7.9 Study Oversight Committee (SOC)

The study will be guided by a group of respected and experienced personnel and trialists as well as at least one 'lay' representative. The SOC will have an independent Chairperson. Face to face meetings will be held at regular intervals, likely to be every six months. Routine business is conducted by email, post or teleconferencing.

The Oversight Committee, in the development of this protocol and throughout the study will take responsibility for:

- Major decisions such as a need to change the protocol for any reason
- Monitoring and supervising the progress of the study
- Reviewing relevant information from other sources
- Informing and advising on all aspects of the study

The membership of the SOC is shown on page 3.

The full remit and responsibilities of the SOC will be documented in the Committee Charter which will be signed by all members.

7.10 Data Monitoring Committee (DMC)

A DMC is not required for this feasibility study. No interim analyses will be conducted. Data will be assessed for completeness rather than analysed for efficacy/effectiveness. Study oversight will be the remit of the Study Oversight Committee.

7.11 Essential Documentation

A Study Master File will be set up according to Warwick SOP and held securely at the coordinating centre.

7.12 Financial Support

The study has been funded by a HEE/NIHR Integrated Clinical Academic Programme Clinical Doctoral Research Fellowship, award number ICA-CDRF-2018-04-ST2-005.

8. MONITORING, AUDIT AND INSPECTION

A Study Monitoring Plan will be developed and agreed by the Study Management Group (SMG) and SOC based on the study risk assessment. Monitoring may be conducted by exploring the study dataset and may include on-site monitoring. In order to assist the sponsor, the ambulance service will develop procedures for internally monitoring the study and to permit direct access to source data during site monitoring visits.

It is not necessary for Ambulance staff participating in the study to complete full GCP training but key elements will be included in the study information package in order to fulfil the HRA recommendation that GCP guidelines are appropriate and proportionate to the study activities undertaken.[49]

Quality assurance checks on eligibility, data collection and consent process will be carried out by a research paramedic (not the researcher) using a WCTU remote monitoring checklist at least once during the recruitment period.

9. PATIENT AND PUBLIC INVOLVEMENT (PPI)

Patient and Public Engagement has been central to the development of this research. A PPI panel was engaged through the South Central Ambulance Service Patient Forum and the Foundation Trust membership during planning and preparation of the grant application for this project. A meeting was convened where the background and ideas for the research were presented. The group could understand and articulated the overarching aim of the project. All agreed it is an important topic and the research is timely. They felt that the research was ethical and the proposed deferred consent approach was appropriate. The risks and benefits for patients of receiving study treatment were discussed with this panel. Overall, they considered that since the intervention energy levels are all used within current UK practice, recruitment into the study posed no greater risk than not being recruited into the study. I jointly drafted the lay summary of the project for the application with two members of the panel. These members wished to retain their involvement with the study and have joined the local PPI advisory panel.

Particular issues we have consulted the advisory panel on were public acceptability of the study, deferred consent and informing survivors and the relatives of non-survivors. On the issue of whether to contact the relatives of non-survivors through active or passive means, opinion was divided amongst the panel. After much discussion, it was decided that a sensitively-worded letter would be drafted with the intention of providing brief information about the study and points of contact for people to find out more if they wished. Further PPI opinion was sought on the wording

of this letter and the general approach including from members of the University Hospitals Birmingham NHS Foundation Trust Clinical Research Ambassador Group and a Patient research ambassador at the Royal Berkshire NHS Foundation Trust. This approach will be monitored throughout the study and amended if it becomes evident that the harms to relatives outweigh the benefits.

Throughout the project, two PPI members will sit on the Study Oversight Committee and we will continue to consult with, and seek the advice of, the PPI local advisory panel.

10. DISSEMINATION AND PUBLICATION

The study protocol will be published in an open-access journal. It will also be available on the university website.

The results of the study will be reported first to study collaborators. The main report will be drafted by the study co-ordinating team, and the final version will be agreed by the Study Oversight Committee before submission to the NHS Research Ethics Committee and for publication in an appropriate healthcare journal, on behalf of the collaboration. Results will be uploaded to the trials registry (ISRCTN). The success of the study depends on the collaboration of doctors, nurses and researchers from across the region. Equal credit will be given to those who have wholeheartedly collaborated in the study. Authorship of any outputs will be determined in accordance with University of Warwick SOP 22 (Publication and Dissemination) and International Committee of Medical Journal Editors guidance on authorship. The study will be reported in accordance with the Consolidated Standards of Reporting Trials (CONSORT) guidelines (www.consort-statement.org). In accordance with funder requirements, the study report will be open access.

Together with our PPI group we will construct an information sheet outlining study results. Participants, their consultees and other interested parties will be offered the opportunity to be notified of the results of the study. Those wishing to receive the results will be sent the information sheet.

Results will be shared at a national conference by members of the study team. We will also attend a local event with our PPI members and present the results of the study together.

